## 2.3 Questionnaires

7 questionnaires will be administered to the parents and children of study participants (see Figure 4). (1) Intake Questionnaire: this is a respiratory/general health questionnaire used by the [REDACTED] Study. (2) Tobacco Questionnaire- this is a short questionnaire from questions used on the National Youth Tobacco Survey. (3) AQI intake & follow up: Intake: there are no existing questionnaires evaluating what parents know about the AQI as pertains to their children with asthma. This questionnaire contains questions from NHANES and BRFSS with modifications. The AQI intake has a section to be completed by the parent to understand the parent's knowledge and practices regarding the AQI. The

intake questionnaire additionally contains a section for the child to complete, which is the AQI follow up questionnaire. The follow up questionnaire was developed by the PI to assess usage of the AQI. **(4)** Asthma Control Test (ACT) and Childhood Asthma Control Test (C-ACT) are validated questionnaires to assess asthma control in the last 4 weeks. **(5)** Pediatric Asthma Quality of Life Questionnaire (PAQLQ(S)) is validated questionnaire that will be interviewer-administered. **(6)** Physical activity questionnaire contains modified questions from NHANES and The Physical Activity Questionnaire for older children and adolescents. **(7)** Shortened respiratory questionnaire (sRHQ): this is a short questionnaire that has been modified from the [REDACTED] study. It is designed to capture asthma exacerbations.

The order of the questionnaires is important. The AQI intake form will be completed by the parent/guardian and the child participant prior to AQI education/intervention.

**2.4 Lung Function Tests:** Spirometry and fractional exhaled nitric oxide (FeNO) will be obtained at entrance and exit visit as secondary measures of control (e.g. forced vital capacity (FVC), forced expiratory volume in 1 sec (FEV1), and FEV1/FVC).

**2.5 Anthropometric measures:** Height and weight will be obtained at the baseline and exit visit, to assess if adherence to AQI potentially alters weight/BMI by increased sedentarism.

**2.6 Urine collection:** as an ancillary to this study, will collect urine for cotinine measurement (nicotine metabolites) and store.

**2.7 Nasal epithelial cells (NEC):** as an ancillary to this study, NEC will be collected and stored for future studies aimed at understanding the effects of outdoor air pollution on epigenetic changes and how a behavioral intervention could alter impacts.

### 3. FUNDING:

The study is funded by the American Thoracic Society Foundation (ATSF) unrestricted pulmonary grant.

## **5. STUDY POPULATION:**

The study will be recruited from and conducted at UPMC Children's Hospital of Pittsburgh (single site). Recruitment will be from pediatric pulmonology and pediatric asthma registry. Preference from asthma registry will be pediatric pulmonology clinic patients.

### **5.1 Inclusion Criteria:**

#### Child participant:

1. Physician diagnosed persistent asthma (mild, moderate, or severe).
2. Aged 8-17 years old (at time of consent)
3. Family home internet access or smartphone access + willingness to download AirNow app on phone

#### Parent/guardian participant:

1. Parent or guardian of the child participant

### **5.2 Exclusion Criteria:**

#### Child participant:

1. Diagnosis of other chronic respiratory disease (e.g. cystic fibrosis, bronchopulmonary dysplasia, etc.)
2. Immunodeficiency- acquired or congenital
3. Neuromuscular disease
4. Disability affecting ambulation (e.g. spastic quadriplegia)
5. Cyanotic congenital heart disease
6. Plans to move out of Pittsburgh area in next 6 months
7. Only 1 participant per household is eligible

#### Parental/guardian exclusion criteria: none

## 6. STUDY INTERVENTION:

All children will receive an asthma action plan (AAP). The asthma action plan lists the participant's daily asthma controller medications and informs patients/families what to do if asthma symptoms. All children will receive the same AQI education, however the intervention group will receive an AAP that has the reviewed AQI material printed on the back (Figure 5). In addition, the intervention group will demonstrate to research coordinator that (1) they can navigate to the airnow.gov website to check the local AQI or (2) they can navigate the AirNow phone app to check local AQI. (see AQI education form)

As mentioned above in Section 2, all patients will receive education about the AQI as we do not wish to withhold potentially valuable information and the consenting process will result in discussion of the AQI. However, the intervention group will be provided the AQI on the back of their AAP whereas the control group will not.

## 7. POTENTIAL BENEFITS:

This protocol will help to determine if improved education and usage of an already publicly available intervention (AQI) reduces asthma exacerbations, improves asthma control and asthma quality of life. If this intervention is effective there will be benefits for pediatric patients with asthma.

Parents and participants will be provided with an asthma action. All participants should already have an asthma action plan as part of their care, however there may be an additional benefit of providing the plan. The results of spirometry or FeNO may be shared with the participant's primary care physician or asthma specialist (per parental request/approval).

## 8. RISKS AND DISCOMFORTS:

### 8.1. Procedures

**Figure 5: Back of AAP + AQI**

**Asthma checklist before going outside:**

- ALWAYS** keep your rescue inhaler (& spacer) handy
- Check the air quality index (AQI):  
airnow.gov **OR** Airnow smartphone app
- Watch for symptoms: cough, wheezing, difficulty breathing, chest tightness.
- If you have symptoms, this is a sign to take it easy. Follow your yellow zone & consider: limiting time outside, increasing the number of breaks, do less intense activities, stop activity, or go indoors.

AQI	AQI #	What to do:
Good	0-50	No action required. A good day to be active outside!
Moderate	51-100	Children who are unusually sensitive to air pollution could have symptoms. If so, take steps to reduce prolonged or heavy exertion.
Unhealthy for sensitive groups	101-150	Ok to be active outside for short activities. For longer activities take more breaks & do less intense activities. Reduce prolonged or heavy outdoor exertion.
Unhealthy	151-200	Move longer or more intense activities indoors. Avoid prolonged or heavy exertion outdoors- a good day to work out in the gym.
Very Unhealthy	201-300	Move activities indoors. Avoid all physical activity outdoors.
Hazardous	301-500	Stay indoors and keep activity levels low. Keep windows closed and avoid frying/broiling on these days.

- Air pollution can make asthma symptoms worse and trigger attacks. Asthma symptoms can happen even on days when the air quality is good. Always keep your rescue inhaler handy.
- Exercising on days when air pollution is bad can mean more air pollution in your lungs. Changing your activity level can help. For example, take a walk instead of a run. Changing how long you spend outside exercising can also help. For example, don't stay outside as long.

**Plan activities when and where pollution is lower:**

- Ozone is usually higher on hot summer days in the afternoon & early evening. On days ozone is high, plan your outdoor activities in the morning.
- Particulate pollution can be higher in certain places. Try to avoid exercising where particles are higher. Examples: near busy roadways, during rush-hour traffic, near industrial areas, and when there is smoke in the air.

*Don't let asthma keep you from being active. The CDC recommends 60 minutes of physical activity a day. If asthma is limiting your activity, talk to your doctor!*

Table 1: Study Procedures

VISIT	LOCATION	QUESTIONNAIRE	EMR	MEASURES	SPECIMENS
1	In-person, PCTRC	Intake, AQI intake, PA, ACT or CACT, PAQLQ, tobacco intake	Confirm asthma controller medications, IgE, allergen testing, eosinophils, BAL or sputum eosinophils	Spirometry, FeNO, height, weight	Nasal epithelial cells, urine
2	Telephone	sRQ, AQI_f/u, PA, ACT or CACT.	-	-	-
3	Telephone	sRQ, AQI_f/u, PA, ACT or CACT.,	-	-	-
4	Telephone	sRQ, AQI_f/u, PA, ACT or CACT.	-	-	-
5	Telephone	sRQ, AQI_f/u, PA, ACT or CACT.	-	-	-
6	Telephone	sRQ, AQI_f/u, PA, ACT or CACT.	-	-	-
7	In-person, PCTRC	sRQ, AQI_f/u, PA, ACT or CACT.	-	Spirometry, FeNO, height, weight	Nasal epithelial cells, urine

Intake questionnaire (completed by parent); AQI intake- includes parent portion (completed by parent) + AQI follow up (completed by participant); PA=physical activity (parent and/or participant), ACT=asthma control test ages 12 and older (completed by participant); CACT=childhood asthma control test for ages 8-11 (completed by parent and participant); PAQLQ(s)-pediatric asthma quality of life questionnaire (completed by participant); participant tobacco intake form (completed by participant); sRQ= shortened respiratory questionnaire (completed by parent); AQI\_f/u=AQI follow up questionnaire (completed by participant).

**8.1a Questionnaires:** the risks from questionnaire administration involves social-psychological risk resulting from inadvertent disclosure of medical information and/or questions may create discomfort. Participants and parents do not have to answer any question that they do not wish to answer.

**8.1b Spirometry:** The risks of spirometry are minimal and include temporary lightheadedness from repeated spirometry maneuvers and there is a small risk (rare) of wheezing and shortness of breath and increased cough when performing spirometry. If the participant has had a pneumothorax (a.k.a collapsed lung, air leak), open thoracic surgery (a.k.a open chest surgery), myocardial infarction (a.k.a heart attack), or hemoptysis (a.k.a coughing up blood) in the last 2 months they should not undergo spirometry.

**8.1c Fractional Exhaled Nitric Oxide (FeNO):** The risks of FeNO are similar to spirometry in that they are minimal may include temporary lightheadedness. If the participant has had a pneumothorax (a.k.a collapsed lung, air leak), open thoracic surgery (a.k.a open chest surgery), myocardial infarction (a.k.a heart attack), or hemoptysis (a.k.a coughing up blood) in the last 2 months they should not undergo FeNO.

**8.1d Nasal epithelial collection:** The main risk of the nasal sample is discomfort and nose bleeding. Additional risks include watery eyes and sneezing. There is also the rare possibility of a tear at the brushing site and infection from this procedure. We will place a small amount of lidocaine (~1cc) into the participants nose to reduce discomfort. Lidocaine will not be injected with a needle (no needles will be used). Lidocaine sometimes cause an unpleasant taste in the mouth and may cause temporary redness, stinging, and swelling at the application

site. If the participant has a bleeding disorder (coagulopathy) they should not undergo nasal cell collection.

**8.1e Urine collection:** the risks of urine collection are minimal and may include discomfort with providing a sample.

**8.1f Measures of height and weight:** possible participant discomfort with having weight obtained. The risks are minimal.

**8.2 Break of confidentiality:** participant data will be identified by a unique study number assigned to each child. The unique study number will be used as identification and not participant identifying information (ex. first name, last name, DOB) will be kept with research information. The link between study ID and participant will be kept in a secure and locked location.

**8.3 Genetic testing:** Genetic testing carries the potential for breach of confidentiality that could have a potential impact on future reproduction plans, insurability, employability, or could have a negative impact on family relationships, and/or result in paternity suits or stigmatization. Information about the child's participation and results will not be placed in the medical record. Participants will not be informed about an individual genetic data to be obtained from the study. Genetic information will never be labeled with a participant's identifying information such as name, date of birth, etc.

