### 2.1 Hypothesis and Specific Aims

We hypothesize that the addition of the AQI to AAP will (A) reduce asthma exacerbations, and (B) improve symptom control & quality of life in children with asthma. To test these hypotheses, in this study we will pursue the following specific aims:

- Aim 1: To recruit a pilot cohort of 40 children with asthma. For proof of concept, we will recruit 40 children with asthma from Children's Hospital of Pittsburgh, the only children's hospital serving southwest Pennsylvania (metropolitan area >2.6 million people). Baseline knowledge about the AQI including familiarity, usage, and prior healthcare provider discussion will be assessed.

- Aim 2: To evaluate if the addition of the AQI to AAP reduces asthma exacerbations in a pilot study of children. Participating children (Aim 1) will be randomized to one of two groups. All participants/caregivers will receive an AAP and verbal AQI education. The intervention group will additionally demonstrate the ability to check the AQI, and AQI recommendations will be incorporated onto their written AAP. Children will be followed monthly for 6 months to evaluate adherence to AQI recommendations and assess the frequency of asthma exacerbations, defined per ATS guidelines. Other known factors contributing to asthma exacerbations, such as asthma severity, viral illnesses, allergic triggers will also be monitored.
- Aim 3: To examine whether the addition of the AQI to AAP improves asthma symptom control and quality of life in a pilot study of children. Asthma symptom control will be measured in participating children monthly, and quality of life will be assessed before randomization and at 6 months. Symptom control and quality of life will be evaluated within (before/after intervention) and between groups.

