### **10. ADVERSE EVENTS:**

#### **10.1 Adverse events**

The risk for adverse events related to the study intervention are minimal. An adverse event will be defined as an unexpected accident, experience, or outcome that is unexpected (in terms of nature, severity, or frequency), is related or possibly related to the subject's participation in the research, and places subjects or others at a greater harm (including physical, psychological, economic, or social harm) than was previously known or recognized. Such events will be recorded as per 45 CFR part 46. Unexpected adverse events of moderate severity will be reported to the IRB within 10 working days of the investigator learning of the event.

As asthma is a chronic lung disease with waxing and waning impairment and risk, asthma exacerbations (both severe & moderate) and loss of control are not unexpected. We will consider an increased severity or frequency of such events as adverse events, although these will not meet the definition required for reporting to IRB as these such events are not anticipated to be related or possibly related to the research.

Specific examples of these are below. While these will not require reporting to the IRB, they will be captured as adverse events and safety procedures will be implemented as below:

1. If a participant has more than 3 severe asthma exacerbations during the study
2. If a participant has 3 consecutive ACT or C-ACT scores  $\leq 19$ .
3. If a participant has an FEV1  $< 80\%$  at either V1 or V7

These events will be recorded, parent or guardian/participant will be notified of possible poorly controlled asthma and will be encouraged to follow up with managing asthma specialist. With parental permission, PI or RC will reach out to managing asthma specialist to alert to concerns.

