## **11.2 Eligibility and Randomization (Visit 1)**

Once the family and participant have indicated willingness to participate and have scheduled a V1, the research coordinator will notify PI. PI will review medical record (granted permission by Asthma Registry patients and allowable access as part of regular duties) to confirm asthma controller medications. PI will prepare AAP for research coordinators to distribute. In the event of a discrepancy between parental reported controller medication and medical record medication, the PI will reach out (with participant parent permission) to healthcare provider managing asthma to confirm asthma controller medications.

After informed consent has been obtained, participant's will be randomized 1:1 by age group. The RC assign random group at time of intervention. Eligibility for lung function tests and/or NEC will be assessed prior to study procedures. Questionnaires will be administered, height and weight will be obtained, lung function tests will be obtained (if eligible), specimens will be collected (if applicable), and AQI education will be provided. For the intervention group only, the AAP containing the AQI information will be provided. The intervention group will demonstrate ability to navigate to either airnow website or airnow app on smart phone. For the control group, an AAP will be provided (containing no AQI information) Both the participants, parents, and research coordinator will know randomization assignment. V1 should not be done if child participant has been sick with respiratory infection in prior 7 days or currently has respiratory symptoms.

If a participant's spirometry demonstrates an FEV1 <80%, the family and participant's managing asthma healthcare provider will be notified. Per family permission, spirometry will be shared with managing asthma healthcare provider. If a participant's FeNO is above 20ppb, with family permission, FeNO will be shared with managing asthma healthcare provider.

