## **11.3 Trial Phase (Visits 2-6)**

The participants will be followed monthly (every 4 weeks, +/- 7 days) with interval follow up telephone calls. Questionnaires will be administered during the telephone calls. Throughout the trial, participants will be reminded that participation in the research study does not replace clinical care. Moderate and severe asthma exacerbations will be asked about on monthly questionnaires. If a participant reports 3 severe asthma exacerbations (so defined by ATS criteria as an event requiring 3 or more days of systemic steroid treatment for asthma or an ED visit/hospitalization during which a steroid was prescribed), the participant's managing asthma healthcare provider will be notified. Additionally, if a participant has more 3 consecutive ACT or CACT scores that are equal to or less than 19, which is the threshold concerning for asthma control, the participant's managing healthcare provider will be notified.

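### The trial's own alerts can prompt controller changes, but the listed procedures check controller medication only at V1, so the within-group V1-V7 tests cannot isolate the AQI plan and differences between arms in treatment change may go unseen

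*Combined protocol and SAP*

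**What the plan says.** **Medication check.** The EMR column of Table 1 (Study Procedures) reads "Confirm asthma controller medications, IgE, allergen testing, eosinophils, BAL or sputum eosinophils" at V1 and holds a dash for V2 to V7. Table 2 has no EMR column. Section 11.2 describes the check as a record review by the PI before V1, "to confirm asthma controller medications. PI will prepare AAP for research coordinators to distribute".

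**Alerts at V1.** Section 11.2 states: "If a participant's spirometry demonstrates an FEV1 <80%, the family and participant's managing asthma healthcare provider will be notified". Spirometry is passed on with family permission. For nitric oxide: "If a participant's FeNO is above 20ppb, with family permission, FeNO will be shared with managing asthma healthcare provider". Under Section 10.1, families of children with low FEV1 are told that asthma may be poorly controlled and "will be encouraged to follow up with managing asthma specialist".

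**Alerts during follow-up.** Section 11.3 begins one rule with "If a participant reports 3 severe asthma exacerbations", in which case "the participant's managing asthma healthcare provider will be notified". A second rule there covers consecutive ACT or C-ACT scores of 19 or less. Section 10.1 lists similar triggers.

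**Other data collection.** Section 2.3 describes the monthly shortened respiratory questionnaire (sRQ in the tables) as a tool for capturing exacerbations and does not reproduce its items. Aim 2 (Section 2.1) names severity, viral illness and allergic triggers as co-factors to monitor. It does not name treatment change.

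**Analysis.** Aim 3 says: "Symptom control and quality of life will be evaluated within (before/after intervention) and between groups". The Statistical Plan adds paired tests of six months minus baseline for each primary outcome. Controller use appears there only in the list of covariates compared between groups. The power paragraph expects the within-group tests to do better than the between-group test for PAQLQ.

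**The concern.** An alert to the provider, or advice to the family to see the specialist, may lead to a change of controller. The first alerts come at time zero of the before/after comparison. A child whose treatment is changed after V1 and who is better at V7 counts as an improvement in the paired test, whatever the AQI plan did. Randomisation does not protect that test.

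Between arms the risk is different. Follow-up alerts are triggered by exacerbations and ACT/C-ACT scores, which are the outcomes. The arm doing worse would receive more alerts and perhaps more treatment review, which would draw the arms together. The trial is also open-label with about 20 children per arm, so controller changes could differ between arms by chance or because families respond differently. With no planned record after V1, a reader of the results could not tell.

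**Working it through.** **1. The plan's own figures.** The power paragraph gives 20 per group, two-sided alpha 0.05, and no SD for these comparisons. With SD = 1 (my assumption) and the noncentral t distribution:
- two-sample, noncentrality d × √(20/2): d = 1.05 gives 89.9%, d = 0.91 gives 80.1%;
- paired, noncentrality d × √20: d = 0.76 gives 89.7%, d = 0.66 gives 79.9%.

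These match the stated 90%, 80%, 90% and 80%, so the plan's differences are in SD units.

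**2. Share of children whose treatment changes.** The documents give no rate. Assume that 30-60% trigger a V1 alert and 25-50% of those have controllers changed: 0.30 × 0.25 = 7.5% (3 of 40) to 0.60 × 0.50 = 30% (12 of 40). I add 50% as an extreme.

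**3. Within-group test, no AQI effect.** Spurious mean change = share p × effect d. Assume d = 0.5 to 1.0 SD of the change score. The rejection rate is simulated, n = 20, baseline SD of change 1.

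| p | d | Spurious change (SD) | Paired test rejects |
|---|---|---|---|
| 7.5% | 0.5 | 0.04 | 5.3% |
| 7.5% | 1.0 | 0.075 | 6.0% |
| 30% | 0.5 | 0.15 | 9.6% |
| 30% | 1.0 | 0.30 | 21% |
| 50% | 0.5 | 0.25 | 18% |
| 50% | 1.0 | 0.50 | about 48% |

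On the ACT scale, using the plan's clinical difference of 2-3 points as a yardstick for one child's gain: 0.075 × 2 = 0.15 to 0.30 × 3 = 0.9 points.

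**4. Between-arm test, same p and d in both arms.** The expected difference is p·d − p·d = 0, and the simulated type I error is 5.0-5.1% in every row above. Noise rises: the SD becomes √(1 + p(1−p)d²), which is √1.21 = 1.10 at p = 30%, d = 1. Power for a difference of 1.05 falls from 89.9% to about 84% there, and to about 82% at p = 50%, d = 1.

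**5. Chance imbalance.** At p = 20%, the SD of the arm difference in number of children changed is √(2 × 20 × 0.2 × 0.8) = 2.5. A 1-SD imbalance is worth 2.5/20 × 2 to 3 = 0.25-0.38 ACT points. An imbalance of 5 or more children has probability about 7%; five children would be worth 5/20 × 2 to 3 = 0.5-0.75 points. For comparison, with the SD of 2 from the plan's repeated-measures calculation, the standard error of the arm difference is 2 × √(2/20) = 0.63 points.

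**6. Outcome-driven alerts.** The documents give nothing from which to size the dilution. They need about three severe exacerbations or at least three consecutive low monthly scores, so they come well into the 24 weeks.

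**The case against.** The strongest reply is that the effect of the AQI plan is the randomised contrast, and the V1 alerts follow one rule in both arms. A reader might infer that these alerts bias that contrast. The documents do not support this: step 4 gives zero expected bias and an unchanged type I error. A reader might also infer that every child's V1 results go to the provider. They do not: notification requires FEV1 below 80%, FeNO must exceed 20 ppb, and passing on spirometry or FeNO needs family permission.

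It is also too strong to say that nothing could show what happened. FEV1, FeNO, ACT/C-ACT and exacerbations are collected, and Section 10.1 records most alert-triggering events as adverse events, so children who met an alert rule could largely be counted by arm. The PI already has chart access for the V1 check, so a later check is not ruled out. The sRQ must cover steroids and rescue medication to classify exacerbations and could hold a controller item.

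The size rests on assumed rates, and the 2-3 ACT points are a clinical difference, not the effect of a controller change. Chance imbalance of the size in step 5 is mostly ordinary sampling noise, already carried in the outcome variance.

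All of this stands. What remains is that no listed procedure or planned analysis covers controller changes after V1, that the before/after tests have no protection from them, and that a table alone would not remove that confounding.

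**Conclusion.** The point holds for the within-group V1-V7 tests: as planned, they cannot separate the AQI plan from controller changes that the trial prompted. Regression to the mean and the AQI education given to both arms add to the same problem. For the between-arm comparison the claim is limited: no expected bias from the V1 alerts, some loss of precision, possible dilution from outcome-driven alerts, and differences in controller change that would go unseen unless the sRQ already records them.

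The size is unknown. Under the assumed 7.5-30% share and 0.5-1.0 SD effect, it runs from negligible (5.3% rejection) to material (21%) for the paired test. This is a cheap improvement that should be made; it does not undermine the randomised design.

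**What to change.** Leave the alert rules as they are, and:
1. Add a fixed question on controller changes since the last contact at each of V2 to V7, or confirm that the sRQ already has one. Repeat the EMR controller confirmation at V7 in Table 1.
2. Log the date and reason of each alert sent to a provider. Sections 10.1 and 11.3 word the triggers differently (more than 3 against 3 severe exacerbations; 3 against more than 3 consecutive low scores). The two passages must be reconciled so that the log has one definition.
3. In the Statistical Plan, tabulate alerts and controller step-ups and step-downs by arm as post-randomisation data. Do not enter them as covariates, because they may themselves be affected by the intervention.
4. State that the within-group before/after tests are descriptive and that the effect of the AQI plan is judged from the between-arm comparison. Amend the power paragraph's remark on PAQLQ to match.

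The cost is a few minutes per contact, 40 repeat chart checks of a kind already done at V1, a short log and one table. In return, the pilot learns how often its own procedures lead to treatment change, which helps in designing the next study.
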